## 1.0 Research Design

### 1.1 Purpose/Specific Aims

The purpose of this study is to determine if music is an effective pain management strategy during IUD insertion.

#### A. Objectives

This study will determine if pain and anxiety scores are lower in subjects with music versus controls without music during IUD insertion.

#### B. Hypotheses / Research Question(s)

This study hypothesizes that music will decrease pain during IUD insertion. We also hypothesize that music will decrease anxiety during IUD insertion.

### 1.2 Research Significance

Throughout the United States, long acting reversible contraceptive (LARC) methods are becoming increasingly popular. According to ACOG, 11.6% of women use LARCs, with 10.3% using intrauterine devices (IUDs) and 1.3% using the contraceptive implant (ACOG, 2017). As LARCs become more common, so should the awareness of difficulties with their insertion. Pain is one of the most frequent complaints regarding insertion among LARC users. Compared to implant users, more IUD users reported insertional pain (80% vs 18%,  $p<0.0001$ ) and less satisfaction with pain management (72.4 vs 85.6,  $p=0.04$ ) (Callahan, 2019).

Very few strategies to minimize pain during LARC placement have been successful. Many providers advise women to take motrin or advil prior to their IUD insertion appointment. However, administration of ibuprofen prophylaxis prior to IUD insertion has not been shown to decrease pain at the time of insertion. (Chor, 2012). Another method that has been explored is a lidocaine block. A randomized control trial of 95 women concluded that a 1% lidocaine paracervical nerve block reduces pain during IUD insertion compared with a sham block with pressure on the vaginal epithelium ( $p<0.001$ ) (Akers, 2017). Other measures to manage pain and increase satisfaction with LARC insertion remain largely unstudied.

This study proposes that music may be effectively used as a pain management strategy. A metaanalysis of 97 randomized control trial ( $n=374$ ) showed music was associated with statistically significant effects in decreasing pain, including acute, procedural, chronic, and cancer pain ( $p<0.00001$ ) (Lee, 2016). Though no studies have looked at the relationship between music and pain during IUD insertion specifically, studies have been done regarding similar procedures, such as colposcopy and manual vacuum aspiration. A metaanalysis of 5 randomized control trials

assessing the effect of music therapy showed no difference in anxiety levels (n=763, p=0.4) or pain (n=649) during (p=0.31) and after (p=0.33) colposcopy. (Abdelhakim, 2019). Similarly, a randomized control trial of 101 women randomized to undergo abortion with routine pain control measures only (ibuprofen and paracervical block) or with the addition of intraoperative music via headphones showed that intraoperative music, in fact, increased reported pain (p=0.045) (Guerrero, 2012). Due to these conflicting reports, our study aims to explore music therapy as a pain management strategy during LARC insertion specifically.

### **1.3 Research Design and Methods**

#### **A. Research Procedures**

This will be a randomized control trial conducted in the gynecology clinic inside Robert Wood Johnson University Hospital (RWJ) and the offices of Rutgers Medical Group Obstetrics and Gynecology (RMG). A family planning attending alone at RMG or accompanied by obstetrics and gynecology (Ob/Gyn) residents at RWJ will perform all IUD insertions during this study period. Patients scheduled for an IUD, either the Mirena® (levonorgestrel-releasing intrauterine system 52 mg) or Paragard® (intrauterine copper contraceptive), at both locations will be instructed to take ibuprofen 30 minutes prior to their procedure.

Enrollment will occur during all weekdays at both RWJ and RMG. Eligible women will be able to read and write in English. Exclusion criteria include contraindications to IUD placement: Active pelvic infection, pregnancy, known distortion of uterine cavity, Wilson's disease (Paragard® only), breast cancer (Mirena® only). Eligible women will be enrolled if they are willing to be randomized. Written consent will be obtained from each participant.

After the consent process is completed, the patients will complete a survey which includes their demographic information, if they are currently menstruating, and their pregnancy history while sitting in the waiting room. The patient will also complete a 10 point visual analog scale (VAS) to report her baseline pain and a State Trait Anxiety Inventory (STAI). Vital signs will be recorded with an automated machine.

Participants will then be randomized to routine pain control measures or routine pain control measures plus music. Randomization will be completed by the study staff, who will open sequentially numbered, sealed, opaque envelopes. Allocation will be in a 1:1 ratio. Routine pain control will include instructions to take ibuprofen 600 mg 30 minutes prior to the procedure. These instructions will be given to all participants. It will be noted whether patients actually take ibuprofen or not by the study staff. Patients randomized to receive music in addition to routine pain control measures, will listen to preselected classical music played on the PI phone. Patients will control the volume.

A study staff member will be present in the room throughout the duration of the procedure in addition to the physician performing the actual insertion of the IUD. This study staff member will complete a procedure information sheet including vitals, type of IUD inserted, and the VAS and STAI at several points of the procedure (immediately prior to the procedure, point of speculum insertion, point of tenaculum placement, point of IUD insertion, and 5 minutes post-procedure).

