#### **1.5 Sample Size Justification**

The goal of this study was to find a change in the pain score that would be clinically relevant. A 2 point reduction in the 10 point VAS was deemed as clinically significant. To detect a difference of at least 2 points with at least 90% power, two sided alpha 0.05, and a standard deviation of 3, this study required at least 48 women per arm.

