**4.3 Number of Subjects**

**A. Total Number of Subjects**

A total of 48 women per arm, or 96 total subjects are necessary to complete this project. We expect that approximately 200 women will need to be screened to successfully enroll 96 subjects.

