**C. Feasibility**

In an average month, 20 women are seen for IUD insertion between both sites (RMG and RWJ). As the study intervention (music) confers no additional risk to routine management during IUD insertion, we anticipate that at least half of these women will consent to participate in the study. If approximately 10 women are enrolled in the study monthly, then we believe it is feasible to complete this study in little over a year.

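### Neither the described allocation nor the planned analysis takes account of site, though the inserting team differs between the two sites; a site term and site-specific envelopes would give a modest gain in precision

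*Combined protocol and SAP*

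**What the plan says.** On allocation, section 1.3 A states: "Randomization will be completed by the study staff, who will open sequentially numbered, sealed, opaque envelopes". It adds: "Allocation will be in a 1:1 ratio". It does not say how the sequence is generated, whether it is blocked, or whether there is one envelope series or one per site.

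On the sites, the same section says: "A family planning attending alone at RMG or accompanied by obstetrics and gynecology (Ob/Gyn) residents at RWJ will perform all IUD insertions". A family planning attending is therefore present at both, and the stated difference is the residents at RWJ. Section 4.3 C gives accrual for the two sites together ("In an average month, 20 women are seen for IUD insertion between both sites (RMG and RWJ") and no figure for each.

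On sample size, section 1.5 takes a 2-point VAS difference "with at least 90% power, two sided alpha 0.05, and a standard deviation of 3" and concludes that "this study required at least 48 women per arm". Section 4.3 A sets the total: "A total of 48 women per arm, or 96 total subjects are necessary to complete this project".

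On analysis, section 6.1 names a t-test and its nonparametric counterpart for pain and anxiety. Site does not enter.

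**The concern.** Who inserts the device, and in which clinic, may plausibly affect insertion pain, although the documents give no figure for this. Site is known before randomization, so it costs nothing to measure. Where a known, possibly prognostic factor enters neither the allocation nor the model, two things follow. The arms can differ in site mix by chance, and between-site variation stays in the standard error. In a trial of 96 women with no surplus over the calculated size, what is at stake is some precision and the face credibility of the one comparison that will be made. Validity is not at stake.

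**Working it through.** **Inputs.** From section 1.5: difference 2, SD 3, two-sided alpha 0.05, power 90%, 48 per arm. From 4.3 A: 96 in total. Assumed, because the documents do not give them: the share of women from each site (50:50 unless stated) and the difference in mean pain between sites, D = 0.5, 1 or 2 VAS points. Section 1.4 says there are no preliminary data to narrow these.

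**1. The plan's own figure.** n per arm = 2(1.960 + 1.282)² × 3² / 2² = 47.3, rounded up to 48. This reproduces. Power at 48/48 is 90.4% by the normal approximation and 89.8% by the noncentral t. The noncentral t is used below. The standard error is 3 × √(2/48) = 0.61.

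**2. Site imbalance with arm sizes fixed.** Suppose the list is fixed at 48/48 but not stratified, with 48 women from each site. The number from one site in the music arm, h, is hypergeometric (96, 48, 48). The difference in site share is d = (2h − 48)/48.
- The SD of d is 10.3 percentage points.
- P(|d| ≥ 10 points) = 30.7%. Attainable values move in steps of 2/48, so this means 27 versus 21 women or worse (12.5 points).
- P(|d| ≥ 20 points) = 6.6%.
- With one site supplying 20% to 50% of women, the 10-point probability ranges from about 24% to 31%.

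**3. Effect on the estimate.** An imbalance d shifts the estimated difference by D × d. At d = 0.208 (29 versus 19 women), the shift is 0.10, 0.21 or 0.42 points for D = 0.5, 1 or 2. Compare the standard error of 0.61 and the target difference of 2.

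**4. Gain from using site.** Treat 3 as the total SD. With site share π, the within-site SD is √(9 − D²π(1 − π)). The third and fourth columns assume 24 per arm at each site. The last column keeps the site term but uses the unstratified 48/48 list of step 2: the standard error is divided by √(1 − d²) and power is averaged over the distribution of d.

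| D | Within-site SD | Standard error | Power, balanced and adjusted | Power, unstratified list but adjusted |
|---|---|---|---|---|
| 0.5 | 2.990 | 0.610 | 90.0% | 89.7% |
| 1 | 2.958 | 0.604 | 90.6% | 90.3% |
| 2 | 2.828 | 0.577 | 92.9% | 92.6% |

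The degree of freedom spent on site does not change the fourth column at this precision. Against 89.8%, the site term alone supplies about 0.5 of the 0.8 points gained at D = 1, and 2.8 of 3.1 at D = 2. At D = 0.5 the total gain is 0.2 points and depends on site also being balanced. With a 25:75 site split, the balanced and adjusted powers are 90.0%, 90.4% and 92.2%.

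**5. Arm sizes, if randomization were simple.** With Binomial(96, 0.5), an exact 48/48 split has probability 8.1%, and a smaller arm of 38 or fewer has probability 5.2%. Power is 89.5% at 43/53, 88.5% at 38/58 and 89.5% on average. The average loss is 89.8 − 89.5 = 0.3 points.

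**The case against.** The strongest reply is that the plan is silent, not unstratified. A set of 48 music and 48 control envelopes, or blocked envelopes for each clinic, would fit everything written in 1.3 A. A reader might infer that women will be randomized without blocking or stratification, and that the chance of exactly 48 per arm is therefore only 8%. The documents do not support that, because they never say the sequence is simple randomization. This part of the objection stands. It does not dispose of the site point, since step 2 already grants a list fixed at 48/48, and 6.1 names an unadjusted test.

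A reader might also infer that site is confounded with music. That does not follow either. Randomization makes chance imbalance neutral in expectation, and the unadjusted t-test's standard error already carries the between-site variance.

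The sites also have much in common. A family planning attending is at both, and section 2.2 places one study team member at every insertion to standardize recruitment, consent and data collection. That narrows the difference. It does not make the inserting team the same, and no size for the remaining effect is given.

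Finally, blocking has a price here. Staff open the envelopes and are in the room, and the headset described in 2.3 is visible, so past allocations are known. Within-site blocks make later allocations easier to guess. This is a fair limit on the remedy, and the fix has to deal with it.

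**Conclusion.** The point holds as a modest improvement to the design. The plan specifies no blocking or stratification by site, and its stated analysis has no site term, although residents take part at one site only. The cost is avoidable variance, not bias. The possible gain is about 0.2 to 3.1 percentage points of power for site differences of 0.5 to 2 VAS points at an equal site split, and less if the split is uneven. Both the site difference and the split are assumptions. Where the gain is large enough to matter, most of it comes from the site term and not from the envelopes. The calculated 48 per arm stands. A stronger reading, that arm sizes might drift far enough from 48 to harm power, is not supported: even under simple randomization the average loss is about 0.3 points.

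**What to change.** In 6.1, replace the unadjusted t-test for the primary pain comparison with a linear model containing arm and site.

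In 1.3 A, state how the sequence is generated. Provide a separate numbered envelope series for RWJ and for RMG, each from a computer-generated list in permuted blocks of randomly varying size. The list should be prepared by someone not involved in enrolment, with block sizes withheld from enrolling staff. This must be settled before the first envelope is opened.

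The result is near balance within site, not an assured 48 per arm. Blocks of 4 leave each site at most 2 women out of balance, so 46/50 at worst over two sites. Mixed blocks of 4 and 6 leave at most 3 per site, so 45/51. Power at those splits is 89.8% and 89.7% without adjustment, so nothing is lost.

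The cost is a second envelope set, one degree of freedom, and some predictability of later allocations, because staff open the envelopes and see who receives music. Varying and concealing the block sizes limits that predictability but does not remove it.

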#### **B. Data Points**

Pain scores will be collected on the VAS; anxiety scores will be collected on the STAI.

**C. Study Duration**  
Each subject will participate only once during their actual outpatient appointment for IUD insertion. The overall duration of this study will be until the prespecified sample size determined based on power calculation is reached. This is estimated to take approximately 1 to 2 years.

**D. Endpoints**  
The primary endpoint is pain scores. The secondary endpoint is anxiety.

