##### **B. Dependent Variables or Outcome Measures**

Pain is the primary outcome measure. Pain will be measured on the VAS. Anxiety is the secondary outcome measure. Anxiety will be measured on the STAI

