**1.9 Data Collection**

**A. Primary Data Collection**

- **Location:** At both RWJ and RMG, data collection will take place within two main areas: the waiting room and the patient exam room.
- **Process of Data Collection:** In the waiting room, patients will complete the demographic survey. They will also complete, the VAS and STAI for their baseline pain and anxiety scores, respectively. If the patient wishes to complete any of these instruments in private, she will be led into an unoccupied patient exam room. In the exam room, the providers will complete the provider survey regarding the patient. The providers will also record vital signs, BMI, and other pertinent medical information. While in the exam room, at several points through the insertion the VAS and STAI will be administered.
- **Timing and Frequency:** The patient survey will be completed once by the patient while she is in the waiting room. The provider survey will be completed once by the provider while the patient is in the exam room. The VAS will be completed by the patient at several points: immediately prior to the procedure, point of speculum insertion, point of tenaculum placement, point of IUD insertion, and 5 minutes post-procedure. The STAI will be completed immediately prior to the procedure and 5 minutes post-procedure.
- **Procedures for Audio/Visual Recording:** There will be no audio or video recordings of the patients.

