**F. Potential Benefits to Subjects**

Music has been previously shown to reduce pain and anxiety related to procedures as well as related to chronic diagnoses. This study seeks to determine if music has this effect during IUD insertion, as well. Patients who take part in this research and are randomized to the intervention group are anticipated to experience a decrease in pain and anxiety during their IUD insertion. We anticipate that this effect will last for the duration of the procedure and that it will reduce pain and anxiety by approximately 25%.

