## 6.0 Data Management Plan

### 6.1 Data Analysis

Power analysis was completed to determine the sample size to be collected for each arm.

The results will be analyzed using t-tests and its nonparametric equivalent to determine if there is a difference in pain and anxiety scores between the two arms.

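### The primary endpoint names no VAS time point, summary or success rule, so the two-sided 5% error rate and 90% power belong to a comparison that is never identified

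*Combined protocol and SAP*

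**What the plan says.** - Endpoint (section 1.3 D): "The primary endpoint is pain scores. The secondary endpoint is anxiety". Section 1.6 B adds only the instrument: "Pain is the primary outcome measure. Pain will be measured on the VAS".
- Readings (sections 1.3 A and 1.9 A): "immediately prior to the procedure, point of speculum insertion, point of tenaculum placement, point of IUD insertion, and 5 minutes post-procedure". A separate waiting-room VAS, taken before randomization, serves as baseline.
- Question (sections 1.1 A and 1.1 B): "This study hypothesizes that music will decrease pain during IUD insertion". Section 4.7 F looks wider: "We anticipate that this effect will last for the duration of the procedure".
- Size (section 1.5): a difference of 2 points, SD 3, two-sided alpha 0.05, at least 90% power, 48 women per arm. The section refers to a single pain score without saying which, and speaks of a change in it.
- Analysis (section 6.1): "The results will be analyzed using t-tests and its nonparametric equivalent to determine if there is a difference in pain and anxiety scores". Nothing is said about time point, summary measure, testing order, multiplicity, or which of the two tests decides.

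**The concern.** An error rate and a power figure have meaning only for a defined test. Here the design calculation is for one test, while the data collection yields several candidates for it. Followed as written, the plan leads to several unadjusted t-tests on the primary outcome. A null result at IUD insertion could be set aside for a significant one at the speculum or tenaculum, and nothing in the plan would contradict that choice. A post hoc choice, or selective reporting of a time point, could then be mistaken for an effect of music.

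The reverse also holds. If music does reduce pain at IUD insertion, the investigators could not show that this was the test they had planned. Sections 1.1 to 1.2 set out conflicting evidence on music, including one trial in which reported pain rose, so the result will need a test that was clearly fixed in advance.

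**Working it through.** **1. The plan's own figure.** Inputs from section 1.5: difference 2, SD 3, alpha 0.05 two-sided, power 90%. Per arm, n = 2 × [SD × (z₀.₉₇₅ + z₀.₉₀) / difference]² = 2 × [3 × (1.960 + 1.282) / 2]² = 47.28, rounded up to 48. The stated figure is reproduced, for one comparison. Power at 48 per arm is 90.4% by the normal formula. By noncentral t it is 89.8% (n = 48.26, so 49 for a full 90%).

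**2. Does any section identify that comparison?** Sections 1.3 D, 1.5, 1.6 B and 6.1 do not. The objective and hypothesis refer to IUD insertion, but the protocol uses that term in two senses. It is one of the five readings, and it is also the whole procedure: section 1.3 C calls the visit an appointment for it, and section 1.9 A places the repeated readings in the course of it. On the second sense, speculum and tenaculum pain are included.

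**3. Error rate under three possible success rules, with no true effect.**

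- One reading decides: 5%.
- All three procedural readings must be significant: no more than 5%, with lower power than for a single reading.
- Any one reading suffices: above 5%. For three independent tests, 1 − 0.95³ = 14.3%. Readings in the same woman are correlated, and the protocol gives no correlation, so a range is assumed.

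For the third rule, trials were simulated with 48 per arm, equicorrelated normal scores, a pooled t-test at two-sided 0.05 at each point, and 200,000 runs per setting:

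| Assumed correlation | 0.3 | 0.5 | 0.7 | 0.9 |
|---|---|---|---|---|
| Any of three procedural points | 13.6% | 12.6% | 10.9% | 8.4% |
| Any of the three, favouring music (nominal 2.5%) | 6.8% | 6.4% | 5.5% | 4.3% |
| Any of four (5-minute score added) | 17.5% | 15.6% | 13.2% | 9.5% |

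Rounding scores to whole numbers and bounding them at 0 to 10 (100,000 runs) changes little: 13.9%, 12.7%, 11.2% and 8.6% for three points.

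**4. Choice of test.** At a single reading, accepting either the t-test or the Mann-Whitney test raises 5% to about 6%, which is minor. With the Mann-Whitney test deciding and normal scores, simulated power at 48 per arm is 88.5%.

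**5. Sensitivity to the SD.** Section 1.5 gives no source for the SD of 3, and section 1.4 states that there are no preliminary data. At 48 per arm and a 2-point difference, an assumed SD of 3.5 gives about 79% power and 2.5 gives about 97%.

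**The case against.** The best reply is that the plan already implies one comparison. The hypothesis concerns pain at IUD insertion, a reading with that name is scheduled, and section 1.5 refers to the score in the singular. This is a fair reading, and under it the error rate is 5%. It does not settle the matter: section 4.7 F expects the effect throughout the procedure, section 1.3 D uses the plural, and no section ties the primary test to that reading.

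A reader might infer from the table that the trial's false-positive rate is 8% to 14%. The documents do not support that. Nowhere do they say that any significant time point counts as success, so the inflation is conditional on a rule the plan neither states nor excludes.

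Nor does it follow that readers could never separate an effect from selection. The protocol lists all five readings. If all are reported, a reader can see the multiplicity and allow for it. The harm arises through a post hoc choice or selective reporting.

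**Conclusion.** The concern holds in this form: the 5% error rate and 90% power are not secured, because the comparison they belong to is not defined. It is not shown that 5% is exceeded. The 8% to 14% range rests on an any-of-three success rule, normal scores and an assumed correlation of 0.9 to 0.3.

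The sample size is not wrong for a single t-test, where power is 89.8% against a target of at least 90%, a trivial gap. It should not be taken to stand whichever test decides, since the rank test gives about 88%. The point is a must-fix despite being conditional, because it concerns the only primary endpoint and a time point chosen after scores are seen cannot be made prespecified later.

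**What to change.** Make a dated amendment before further enrolment. Failing that, make it before anyone reviews scores by arm, and disclose what had been seen. Timing matters because study staff open the envelopes and record scores in the room, and section 1.3 A describes no blinding; waiting until just before formal analysis may be too late.

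1. In sections 1.3 D, 1.6 B and 6.1, name one primary comparison, for example the VAS score at the point of IUD insertion, music versus control, two-sided 0.05. State whether it is the raw score or the change from the waiting-room baseline.
2. In section 6.1, name the t-test as the deciding test and the rank test as a sensitivity analysis. If the rank test is to decide, restate power as about 88% for normal scores.
3. In section 1.5, state that the 2-point difference and the SD of 3 refer to that score, and label the SD as an assumption.
4. Make the other procedural scores and the 5-minute score secondary, and do not count the pre-procedure score as an efficacy outcome.

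This costs a few sentences, with no extra data or patients. The downside is that the other time points are no longer confirmatory.

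The alternatives cost more. Keeping all three procedural points with a Bonferroni correction (0.05/3) leaves about 79% power per comparison at 48 per arm; 90% would need 61 per arm by the normal formula or 63 by noncentral t. A mean of the procedural scores would need its own justified SD and threshold before 48 per arm could be claimed for it.
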